### **6.4 Comorbidity**

At baseline participants are asked to provide information about comorbid conditions they may be suffering from including how long they have had the condition, whether it is being treated at present, and whether the treatment provides satisfactory control/relief.

### **6.5 Concomitant medications**

Participants are asked to provide the following details at baseline, to ensure they are not contraindicated to receipt of collagenase;

- Use of anticoagulants, for reasons other than a diagnosed coagulation disorder
- Use of anti-platelet agents
- Use of tetracycline antibiotics in previous 14 days

At baseline they are also asked to provide the following details regarding their use of concomitant medications;

- Name of medication
- Reason for use
- Dose
- Frequency
- Route of administration

- Date they started using the medication (if known)
- Date they stopped using the medication (if known and use is not ongoing)

At the four post treatment follow ups they will provide an update about their use of concomitant medication since the previous follow up.

## 6.6 Condition details and clinical assessment

At baseline participants undergo a brief clinical assessment which will, in addition to their goniometric measurements and patient reported assessments, provide an overall summary of the current state of their condition.

- Digits and joints currently affected
- Number of digits/joints affected on the hand/digit being treated as part of the study
- Joint that will be used as the designated study reference digit

## 6.7 Adverse Events

An adverse event (AE) is defined as any untoward medical occurrence experienced by any DISC study participant, which may or may not have a causal relationship with the study treatment. An AE is defined as a serious adverse event (SAE) if it fulfils one, or more, of the following criteria;

- Resulted in death
- Was life threatening
- Resulted in inpatient hospitalisation or prolongation of existing hospitalisation
- Resulted in persistent or significant disability or incapacity
- Resulted in congenital anomaly or birth defect
- Required a surgical or medical intervention to treat/prevent any of the above

All SAE/AEs will be reported and followed up using SAE/AE report forms. The following data are collected;

- Whether or not the AE/SAE was a complication associated with the study treatment
- Specific information about the AE/SAE
- Action taken/treatment given
- Date of onset
- Date of remission (if not ongoing)
- Outcome
- Treatment received
- Relationship to study treatment
- Expectedness
- Seriousness

- Details of death
- Follow up details

## 7. Data management

### 7.2 Data

#### 7.2.1 Data capture

Data is principally collected on paper CRFs, completed by both the study participants and investigators. A copy of the CRFs with the variable names from the database (known as 'specs') are kept by the Trial Statistician in the Statistical Master File. The paper CRFs approved for DISC are as follows;

- Confirmation of eligibility CRF (completed during baseline visit)
- Participant baseline CRF
- Investigator baseline CRF
- Supplementary baseline joint measurements CRF
- Participant pre-treatment CRF (completed during treatment delivery visit)
- Treatment delivery CRF
- Participant week 2 CRF
- Participant week 6 CRF
- Participant month 3 CRF
- Investigator month 3 CRF
- Participant month 6 CRF
- Investigator month 6 CRF
- Participant month 12 CRF
- Investigator month 12 CRF
- Participant month 24 CRF
- Investigator month 24 CRF
- Investigator month 3/6/12/24 supplementary outpatient hospital visits CRF
- Investigator month 3/6/12/24 supplementary inpatient hospital visits CRF
- Investigator month 3/6/12/24 supplementary accident and emergency visits CRF
- Supplementary concomitant medication CRF
- Adverse event initial report form
- Serious adverse event initial report form
- Adverse event follow up form

There will also be a set of photographic data comprised of sets of three photographs of the study reference hand taken by the study investigators during clinic visits at the following time points;

- Baseline

- Pre-treatment
- 3 months post treatment
- 6 months post treatment
- 12 months post treatment
- 24 months post treatment

For participants consenting to participation in the photography sub study, there will be an additional five sets of photographs taken by the participant at baseline and at 3, 6, 12 and 24 months post treatment.

## 8. Analysis

All analyses will be conducted following intention to treat principles on a locked dataset using the latest available version of Stata. Continuous data will be summarised in terms of the non-missing sample size, mean, standard deviation, median, interquartile range and range, and categorical data will be summarised in terms of frequencies and proportions. The primary objective of the analysis is to investigate whether there is sufficient evidence to reject the hypothesis that outcomes (as measured by the 11 items in part 2 of the PEM) at 12 months post-treatment among patients randomised to collagenase are inferior to those of patients randomised to surgery, assuming a non-inferiority margin of 6 points. This assessment will be primarily based on whether the upper limit of the two-sided 95% CI for the difference between treatments at 12 months post treatment obtained from the primary analysis model (see Section 8.2) is greater than 6. One of the key secondary objectives is to compare the extent to which the correction achieved following treatment is maintained over the 12 months following treatment. This will be assessed by comparing rates of recurrence at 12 months post-treatment, where recurrence at 12 months is defined as a reduction in passive extension of 20 degrees between 3 and 12 months post-treatment (see Section 5.6.1). We will investigate whether there is sufficient evidence to reject the hypothesis that collagenase is inferior to surgery in terms of rates of recurrence at 12 months post-treatment, assuming a non-inferiority margin of 10%. This assessment will be based on whether the upper limits of the two-sided 95% CIs for the absolute differences in recurrence obtained from the fitted model (see Section 8.4.7) are less than 10%, and associated one-sided hypothesis tests of  $H_0: d \geq 10\%$ , where  $d = \Pr(\text{Recurrence} \mid \text{Collagenase}, X) - \Pr(\text{Recurrence} \mid \text{Surgery}, X)$  for various pre-specified representative covariate patterns  $X$ .

### 8.1 Baseline data

Baseline data will be summarised descriptively by trial arm and overall, both as randomised and as analysed. The “as randomised” population will include all participants who were randomised, but will exclude any ineligible patients randomised in error (likely to be none or very few patients). The “as analysed” population will include all participants whose data contributes to the primary analysis model (i.e. all participants who provide primary outcome data at one or more post-treatment time point). Brief baseline characteristics and treatment status of just the participants not included in the primary analysis will be presented by treatment group. No formal inferential comparisons of baseline data between

groups will be undertaken. Templates of tables used to summarise baseline data are given in Appendix D.

## **8.2 Primary outcome analysis**

The primary outcome for DISC is patient reported disability (0 – 100%) at 12 months post treatment as measured using the 11 items in part 2 of the PEM (the Hand Health Questionnaire). This section describes the analysis of PEM scores, with the scoring procedure described in detail in Section 5.1.1.

### **8.2.1 PEM completion**

Participants randomised to surgery will tend to wait substantially longer between baseline and treatment delivery. Hence we expect the data to show some degree of systematic imbalance with respect to time elapsed since baseline. The possible influence of this differential delay has been accounted for by referencing the follow-up data collection to the point of treatment delivery. Any changes in the primary outcome between baseline and treatment delivery due to natural progression of the disease are captured by inclusion of a measurement of the primary outcome at treatment delivery. Between group differences in the timing of treatment and follow up will be explored using tabular and graphical summaries as follows:

- A table of the time elapsed between randomisation and PEM completion at each time point by trial arm.
- Plots of time elapsed between randomisation and PEM completion at treatment delivery
- A table summarising the time elapsed between treatment and PEM completion at each post treatment time point (by trial arm), including the proportion of participants completing the PEM within the windows for completion specified in the protocol (+/- 14 days at 3 and 6 months, +/- 3 months at 12 and 24 months).
- Box plot of time elapsed between treatment and PEM completion at 12 months by trial arm.

We will also report the number/proportion of returned participant questionnaires and the number/proportion for which a valid score for the primary outcome could be calculated, as well as a summary of the different patterns of missingness and the frequency with which they occur. Templates of tables described in this section are given in Appendix E-1.

### **8.2.2 Unadjusted primary outcome summaries**

While the primary analysis will be based on the estimated difference between treatments at 12 months obtained from the primary analysis model (see section 8.2.3), we will also present unadjusted summaries of PEM scores at each time point;

- Table of unadjusted PEM scores at each time point including all participants with valid PEM data at these time points together with unadjusted differences and two-sided Wald 95% CIs
- A plot of unadjusted mean PEM score against categorised time point (baseline, pre-treatment, 3, 6, 12 and 24 months) by treatment group

- A plot of unadjusted difference in mean PEM score against categorised time point (baseline, pre-treatment, 3, 6, 12 and 24 months) together with Wald 95% CIs for the difference between groups

Unadjusted estimates of between group differences in PEM scores will be included in a table with the results of the other analyses of the primary outcome. A template of this table is given in Appendix E-2.

### 8.2.3 Primary analysis model specification and fitting

The model fitted for the primary analysis will include all post treatment PEM scores as outcomes, modelling these using a covariance pattern model. This model will be comprised of three levels with post treatment measurement occasions ( $i = 1, 2, 3, 4$ ), nested in participants ( $j$ ), nested in centres ( $k$ ). Details of the terms included in the model are given in Table 2.

**Table 2:** Terms included in the primary analysis models. Fixed effect terms for treatment by time interactions will also be included.

Term	Interpretation	Type	Details
$\text{treat}_{jk}$	Randomised treatment group (collagenase or surgery) of the $j$ th participant at recruitment site $k$	Binary fixed effect	Indicator variable Surgery = 0, Collagenase = 1
$\text{time}_i$	$i$ th post randomisation time point	Categorical fixed effects	4 levels ( $i = 1, \dots, 4$ ) Included in model via 3 dummy indicator variables.
$\text{baseline}_{jk}$	Baseline PEM score of the $j$ th participant at recruitment site $k$ (assumed linear relationship with outcome)	Continuous fixed effect	Percentage disability (0 – 100). Missing scores will be imputed with a predicted score via regression of the observed PEM scores on the observed baseline MHQ scores and reference joint (MCP or PIP). If MHQ score is missing then baseline URAM score will be used in an analogous manner. If URAM is also missing then the reference joint strata specific mean of the observed baseline measurements will be used.
$\text{joint}_{jk}$	Designated study reference joint (MCP or PIP) of the $j$ th participant at recruitment site $k$	Binary fixed effect	Indicator variable MCP = 0, PIP = 1
$u_k$	Random intercept for recruitment site $k$	Random effect	Normally distributed with mean 0 and variance $\sigma_k^2$ . Independent across centres
$\epsilon_{ijk}$	Residual error (conditional on $b_k$ ) of the $i$ th measurement of the $j$ th participant at recruitment site $k$	Error term	$\epsilon_{jk}$ follows a multivariate normal distribution with mean 0 and covariance matrix $\Sigma_{jk}$

This model will be fitted with restricted maximum likelihood estimation, assuming an unstructured covariance matrix  $\Sigma_{jk}$ , with degrees of freedom being calculated using the method of Kenward and Roger [8]. As discussed, delay between baseline and treatment delivery differs between the two arms, with participants in the surgery arm generally waiting longer between the two time points. A sensitivity analysis investigating the possible impact of this on the results of the primary analysis is specified below (see Section 8.3.2).

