## **3. Sample size**

The primary outcome for DISC is the score obtained for the 11 items in part two of the PEM at 12 months post treatment. Previous survey data collected from a representative sample of 880 patients with Dupuytren's Contracture showed the standard deviation of the scores for the 11 items in part 2 of

the PEM at baseline to be 22 points (unpublished). We estimate that a 6 point difference on the PEM at 12 months post-treatment is the threshold at which differences become relevant to the patient, and represents an appropriate non-inferiority margin. An effective sample size of 568 participants (284 per arm) is required to obtain 90% power to assess non-inferiority of collagenase based on the upper limit of a two sided 95% confidence interval (CI) (equivalent to a one-sided 97.5% CI) for the treatment difference ( $\delta = \text{collagenase} - \text{surgery}$ ) at 12 months post treatment, assuming a non-inferiority margin of 6 points and a standard deviation of 22 points. This calculation is based upon the sample size needed for 90% power in a one-sided independent samples t-test of size 2.5%, of  $H_0: \delta \geq 6$  vs  $H_1: \delta < 6$ , ignoring informative baseline covariates (reference joint and baseline PEM score). If  $\delta = 6$ , then we would expect the null hypothesis that collagenase is inferior to surgery to be rejected in 2.5% of hypothetical repetitions of the trial. If  $\delta = 0$ , then we would expect the null hypothesis that collagenase is inferior to surgery to be (correctly) rejected in 90% of hypothetical repetitions of the trial (assuming an analysis based on a one sided independent samples t-test of size 2.5%). Assuming 20% attrition at the 12 month follow up, the total target sample size is 710.

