### 8.3.1 Missing data

The model used for the primary analysis assumes that missing outcome data are missing at random (MAR) conditional on the fixed effects and non-missing outcomes included in the model. We will use multiple imputation to relax this MAR assumption by imputing missing values conditional on additional pre and post randomisation variables. We will also conduct analyses to investigate the sensitivity of the results to various systematic departures from MAR.

We will initially explore whether there are any obvious patterns of missingness in relation to outcome or baseline characteristics. Reasons for withdrawal and timing of withdrawal will be summarised to examine the extent to which withdrawal is driven by mechanisms plausibly related to outcome and/or treatment allocation. Unadjusted mean PEM score trajectories will be plotted for participants dropping out at each time point (both in aggregate and by allocation).

Associations between key baseline characteristics and missing outcome data and/or withdrawal prior to treatment will be explored using three sets of Firth logistic regression models [9]. Missing values of continuous baseline covariates will be mean imputed when fitting these models. The following baseline characteristics will be assessed

- Age (continuous)
- Sex (male or female)
- Smoking status (current, previous or never)
- Alcohol use (does drink alcohol or doesn't drink alcohol)
- Previous treatment with either limited fasciectomy or collagenase (previous treatment or no previous treatment)
- Presence of comorbidities (Yes or No)
- Number of digits affected (treated as continuous)
- MHQ score (continuous)
- URAM score (continuous)
- EQ-5D general health VAS score (continuous)

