#### **8.4.5 Single Assessment Numeric Evaluation Score**

Participants are asked to provide a SANE score at baseline, 2 and 6 weeks post treatment and 3, 6, 12 and 24 months post treatment. These scores will be analysed using a similar covariance pattern model as used for the primary analysis, with the estimated differences in means (and two-sided 95% CIs) at each time point being reported. This model will include participants with a SANE score for at least one post-randomisation time point (i.e. those with no post-randomisation SANE measurements will be excluded). Any missing baseline SANE scores will be imputed with predicted values via regression of the observed baseline SANE scores on observed baseline PEM scores and study reference joint (MCP or PIP). If baseline PEM score is also missing then missing baseline SANE scores will be imputed with predicted values via regression on the observed baseline MHQ scores and reference joint. If baseline MHQ score is also missing then missing baseline SANE scores will be imputed with predicted values via regression on the observed baseline URAM scores and reference joint. If baseline URAM score is also missing then missing baseline SANE scores will be imputed with the reference joint strata specific means.

The fitted model will be checked using the same techniques used for the primary analysis. Should any of these diagnostics suggest serious violation of the model assumptions, then the outcome data will be log transformed (with a value of 0.1 added to scores prior to transformation to allow for scores of 0) and the model refitted. If serious violation of the model assumptions persists, then the SANE scores at each post-treatment time point will be modelled in isolation, using a univariate mixed effect linear regression models, adjusting for allocation, reference joint type (the stratification factor) and baseline SANE score as fixed effects, and centre as a random effect. Mixed effect generalised linear models with log link will be used if model assumptions remain severely violated.

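### The primary model holds the baseline PEM and reference joint effects constant over all four visits; if they change, dropout that depends on baseline differently by arm can bias the 12-month contrast in either direction

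*SAP*

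**What the plan says.** SAP section 8.2.3, Table 2, lists the terms of the primary covariance pattern model. Baseline PEM is one continuous fixed effect, described as "assumed linear relationship with outcome", and reference joint is one binary fixed effect. Both are indexed by participant and site, not by visit. Time has four levels ("Included in model via 3 dummy indicator variables"). The one interaction stated is in the table caption: "Fixed effect terms for treatment by time interactions will also be included". The model is fitted by restricted maximum likelihood, "assuming an unstructured covariance matrix".

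Non-inferiority is judged on "whether the upper limit of the two-sided 95% CI for the difference between treatments at 12 months post treatment" (section 8) against the 6-point margin. Section 8.3.1 says that the model assumes that "missing outcome data are missing at random (MAR) conditional on the fixed effects and non-missing outcomes included in the model".

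The same form is carried to the secondary outcomes. For SANE, section 8.4.5 says "These scores will be analysed using a similar covariance pattern model as used for the primary analysis", which puts one baseline slope across six visits from 2 weeks to 24 months.

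**The concern.** A likelihood analysis that is missing-at-random given its covariates protects the 12-month contrast only if the mean model is right at 12 months. One common slope is a weighted compromise over four visits. If the true slope at 12 months differs from it, the model adjusts wrongly for baseline at that visit. The error cancels while the arms have the same baseline distribution among those observed. It does not cancel once dropout has selected on baseline differently in the two arms. An error in the 12-month joint effect works the same way, through a difference in the share of PIP joints among those observed.

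Differential selection is possible here: the arms are unblinded, waiting times differ (sections 8.2.1 and 8.3.2), and patients with no post-treatment PEM leave the primary model (section 8.1). What is at stake is the contrast that is compared with the margin.

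**Working it through.** **1. The plan's own figure.** Section 3 works with "assuming a non-inferiority margin of 6 points and a standard deviation of 22 points", one-sided 2.5% and 90% power. The normal approximation gives 2 x (22/6)^2 x (1.960 + 1.282)^2 = 282.5, so 283 per arm. The exact t-test power is 0.8995 at 283 and 0.9005 at 284, so 284 per arm (568) is right, and 568/0.8 = 710. The planning standard error is 22 x sqrt(2/284) = 1.846.

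**2. When bias arises.** Datasets were simulated with loss depending only on baseline PEM. The Table 2 fixed effects with unstructured covariance were fitted with common and then with visit-specific baseline effects (maximum likelihood, no centre effect). Bias is the paired difference in the 12-month contrast. Assumptions not in the SAP: average slope about 0.45, residual correlation 0.6, 20% lost by 12 months in each arm, 100,000 participants per scenario.

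- Same slope at every visit: 0.00-0.02, even with a dropout odds ratio per SD of baseline of 3 in one arm and 1/3 in the other.
- Same dropout dependence in both arms: 0.03 or less, whatever the slopes.
- Both conditions broken (points; ranges span different timings of loss):

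| Baseline slope, first to last visit | OR 1.5 vs 1 | OR 1.5 vs 1/1.5 | OR 2 vs 1/2 |
|---|---|---|---|
| 0.50 to 0.35 | 0.04 to 0.11 | 0.08 to 0.21 | 0.14 to 0.38 |
| 0.60 to 0.35 | 0.13 to 0.23 | 0.22 to 0.47 | 0.33 to 0.74 |
| 0.60 to 0.20 | 0.20 to 0.41 | 0.45 to 0.84 | 0.70 to 1.27 |
| 0.25 to 0.55 | -0.15 to -0.29 | -0.30 to -0.65 | -0.51 to -1.03 |

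Swapping the arms reverses every sign. With visit-specific terms the bias was about 0 within Monte Carlo error (SE about 0.14) in nearly all scenarios.

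**3. Other settings** (residual SD 18, residual correlation 0.65, about 20% lost).

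- Opposite dropout (log-odds +/-0.02 or +/-0.03 per PEM point) or dependence in one arm only (0.04): absolute bias 0.38-0.57 with slopes 0.30/0.40/0.45/0.45, and 0.74-1.20 with 0.20/0.35/0.50/0.50. For scale, 0.04 per point is an odds ratio of exp(0.04 x 22) = 2.4 per SD of 22.
- Same direction, different strength (0.02 vs 0.01 per point): about 0.09 with the milder slopes and 0.17-0.19 with the stronger.
- Gently falling slopes 0.45/0.45/0.40/0.30: at most 0.19, even under +/-0.03.

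Slope error times baseline imbalance is not the whole bias. In one mild-slope case it gives about 0.26 where the fitted bias is 0.36; the rest is carried over from other visits through the residual covariance.

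**4. Effect on the decision.** Lower PEM is better, so a bias b towards collagenase gives a one-sided error at a true difference of 6 of Phi(-1.96 + b/1.846). Away from collagenase the sign of b changes. Power at a true difference of 0 is then Phi(6/1.846 - 1.96 - b/1.846), which is about 90% at b = 0.

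| b (points) | Error, towards collagenase | Error, away | Power, away |
|---|---|---|---|
| 0.1 | 2.8% | 2.2% | 89% |
| 0.2 | 3.2% | 1.9% | 88% |
| 0.5 | 4.6% | 1.3% | 85% |
| 0.7 | 5.7% | 1.0% | 82% |
| 1.1 | 8.6% | 0.5% | 76% |

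**5. Reference joint** (illustration, not simulated). An error of 3 points in the 12-month joint effect, with a 10-percentage-point difference between arms in PIP share among those observed, gives 3 x 0.10 = 0.3 points.

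**The case against.** Four points can be made for the plan.

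- **Nothing is misstated.** Section 8.3.1 states an assumption about missingness; it does not claim that the model is valid whatever its mean structure. A correct mean model is a background condition of any regression. This stands: the point concerns a modelling choice, not a contradiction.
- **Bias is not shown for this trial.** The SAP gives neither slopes by visit nor dropout patterns. The large figures need worse-scoring patients to leave one arm and better-scoring patients the other, or strong dependence in one arm only. This also stands, and is why the milder range belongs beside them.
- **Early recovery is a weak argument for PEM.** Its first post-treatment measurement is at 3 months, and MHQ has only 12 and 24 months. The argument applies with most force to SANE, which has no margin. Slope change between 3 and 24 months remains plausible, but is unproven.
- **Planned analyses would help to show it.** The 12-month-only analysis of covariance at sensitivity parameter 0 (section 8.3.1) has its own 12-month slope. The wide-format imputation by arm frees the slopes in the imputation step. Both are sensitivity analyses. The first drops the other visits, so a discrepancy could not be traced to this cause; the second is then analysed with the constrained model. The other refits in 8.3.1 and 8.3.2 keep the constraint. The single-visit fallback in 8.2.4 depends on a residual-versus-fitted plot and a quantile plot, neither of which is aimed at slope change over visits.

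**Conclusion.** The model as written can bias the 12-month contrast, but only when two things hold together: the effect of baseline PEM or joint changes across visits, and dropout depends on that covariate differently by arm. Under assumed inputs the size is about 0.1-0.2 points in mild cases, 0.3-0.7 in moderate ones, and above 1 only with strong slope change and strong opposite dropout. In error at the margin, 0.1 to 1.1 points towards collagenase means roughly 3-9% instead of 2.5%.

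A reader might infer that arm-differential dropout explained by baseline is enough to bias the result, or that the bias favours collagenase. The documents support neither: with constant effects the bias is zero, and nothing in the SAP fixes its direction. The mechanism is well established; its size in this trial is unknown. The point is a worthwhile improvement at almost no cost, not an error in the SAP.

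**What to change.** In Table 2, add baseline PEM by time and reference joint by time as fixed effects, and state that the missing-at-random argument in 8.3.1 relies on them. Use the same form in the refits in 8.3.1 and 8.3.2 and, with each outcome's own baseline, in the URAM, MHQ, SANE and joint-measurement models.

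The cost is one line of text and 3 + 3 = 6 parameters in the primary model, against 568 effective participants. No new data are needed. The sample size is unchanged, because section 3 ignores covariates.
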